1.0 Objectives

1.1 Study Objectives

The specific objective of this proposal is to utilize the practice of telemedicine via connected health devices to enable the guided performance of a remote pulmonary function test (rPFT) in the home. The rationale for this study is to determine whether telemonitoring of respiratory health can help exceed standards of ALS care.

Part 1: Demonstrate the reliability of remote pulmonary function testing, performed via telemedicine, for monitoring respiratory function in patients with amyotrophic lateral sclerosis (ALS)

Primary Hypothesis: There is no difference in the results of PFT and rPFT for respiratory assessment of FVC and MIP.

Secondary Hypothesis: The respiratory therapist, patient, and caregiver will express confidence in conducting the rPFT, as determined by surveys of procedure acceptance.

Part 2: Weekly remote pulmonary function testing (rPFT) and nurse respiratory health coaching (NRHC) in ALS telemedicine

This part randomizes subjects into two arms – both perform weekly rPFT testing and one receives monthly NRHC.

Aim 1: Clinically-meaningful benefit of weekly rPFT

Primary Hypothesis: Home respiratory assessment enables thresholds for non-invasive ventilation (NIV) recommendation to be met on average 30 days sooner when measured weekly compared to the standard 3-month interval.

Secondary Hypothesis: Determine the factors associated with adherence to weekly rPFT procedures.

Aim 2: The impact of NRHC on patient outcomes

Primary Hypothesis: Patient and caregiver teams in the NRHC arm report higher self-efficacy in the respiratory management of the disease at 6 months compared to those in the non-NRHC arm.

Secondary Hypotheses: Patients in the NRHC arm report higher self-efficacy at 12 months, experience less decline of respiratory-related quality of life and fewer respiratory complications compared to those in the non-NRHC arm.

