1.2 Primary Study Endpoints

Part 1: The primary endpoint is completion of a standard PFT and an experimental rPFT during a single clinic appointment. At the endpoint, study outcomes will include:

- 1) The best forced vital capacity (FVC) and maximal inspiratory pressure (MIP) results from that visit's PFT
- 2) The best FVC and MIP results from that visit's rPFT
- 3) Survey responses from study participants.

Part 2: The primary endpoint for Aim 1 occurs at the clinic visit following initiation of NIV. At this time, participants will have had weekly measurements of FVC and MIP from self-administered rPFT procedures, as well as standard PFT assessments performed with the assistance of the respiratory therapist at approximately three-month intervals during standard in-person or telehealth clinic appointments. The primary endpoint for Aim 2 will be the change in self-efficacy scores from baseline. Changes will be compared across arms.

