During each guided rPFT administration, a member of the research team and/or respiratory therapist will guide the patient and caregiver through three valid maneuvers of the FVC and MIP tests. The participants prepare the spirometer by connecting it to the tablet and opening the associated application. The patient is told to sit as upright as possible for the measurement of FVC. They will be told that to do this they will 1) inhale maximally, 2) exhale as hard and fast as possible, and 3) continue to exhale until indicated by the therapist. The researcher will also demonstrate this procedure to the patient. The caregiver applies nose clips to block airflow through the nose, holds the turbine of the spirometer to the patient's mouth and performs three repetitions of this sequence, with periods of relaxation between testings. Testing is repeated until three valid maneuvers are achieved. The application on the tablet computes the FVC and percentage predicted value, the best of which is retained.

To perform the MIP test, the participant inserts the mouthpiece into the pressure meter. The patient is told they will be asked to draw breath in as quickly and powerfully as possible, for at least one second. The researcher tells the caregiver to place a finger over the valve outlet so that no air flows through the mouthpiece during inhalation. Nose clips will be used. The patient performs three repetitions of this task. The maximal negative pressure from a valid run is recorded.

Each piece of reusable equipment will be labeled with an identification number. A log of all loaned materials will be maintained by the researchers. This log, included in the supporting documents, will be maintained on REDCap. Before delivery of the system to the study participant, each piece of equipment will be inspected and tested. This study will not collect prior medical therapy relevant to the use of the device. There are no restrictions on medicines or therapies used by the participants in this study.

Randomization (Part 2 only)

An unblinded blocked minimization method will randomize participants based on demonstrated factors affecting prognosis [Chio2009]. These include: time since diagnosis, age at consent, most recent FVC, and FVC slope from up to the previous year, if available.

NRHC protocol (Part 2 only)

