7.2 Study Procedures

7.2.1 Part 1

On or before the date scheduled for Study 1, a member of the research team who is not part of the ALS clinical team will describe the procedures and receive written informed consent from the patient and caregiver dyad, as well as the respiratory therapist. The participant team undergoes the initial in-person pulmonary function testing, followed 2-3 hours later at the end of the clinical visit by the rPFT. rPFT administration is described in Section 7.4.2. For roughly half of the enrolled participants, the order of assessments is reversed. Following the study procedures, the therapist and patient/caregiver dyad will complete a survey concerning the ease of use and confidence in the rPFT assessment.

Part 1 includes the recruitment of up to 20 practice control participants for validation of the study procedures. They will perform the same procedures as the patient and caregiver, in conjunction with the respiratory therapist.

7.2.2 Part 2

Following consent, the researcher will collect demographic and clinical information: date of birth, gender, time since symptom onset, ALSF Functional Rating Scale - Revised, PFT history, and region of symptom onset. The researcher will guide the subject through completion of the respiratory health questionnaire and self-efficacy assessment.

Subjects consented on the day of their in-person clinic visit will be sent home with an rPFT kit and scheduled for weekly training appointments with a member of the research team. For patients consented remotely, the research team will ship a kit and schedule them for weekly training appointments.

The weekly schedule following the first site visit at week 0 is shown in **Error! Reference source not found.** Weekly training sessions will be guided through the telehealth interface by a member of the research team. If by the 4th training session the participant is able to complete rPFT procedures without guidance as determined by the researcher-completed aptitude assessment, and achieve an FVC result within 10% of the average value from the first three sessions, the participants will be randomized to one of the two study arms.

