8.3 Statistical methods

Part 1: The primary hypothesis is that there is no difference in the results of PFT and rPFT for respiratory assessment of FVC and MIP. We will use a paired sample t-test to determine if the mean test results are comparable between the standard and experimental treatments. We will conduct a qualitative analysis to determine whether the patient, caregiver, and therapist determine the rPFT to be an effective way to conduct tests of breathing function.

Part 2: Aim 1 will be analyzed to determine if the study date of NIV initiation is at least 30 days sooner based on rPFTs compared to standard clinic PFTs. This will be done using a non-parametric two sample test of means, the Wilcoxon-Mann-Whitney rank sum test. For analysis of Aim 2, a linear mixed effects model will be used to analyze the change from baseline between study groups of self-efficacy scores and respiratory health [Verbeke2000]. The effect size will be quantified from the model using the difference in means between the groups with their associated 95% confidence intervals.

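### Section 8.3 describes the Aim 2 mixed model as a comparison of change from baseline and names no baseline term; stating one would usually sharpen the estimate at almost no cost

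*Combined protocol and SAP*

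**What the plan says.** Section 8.3 gives the Aim 2 analysis two sentences: "a linear mixed effects model will be used to analyze the change from baseline between study groups of self-efficacy scores and respiratory health", and "The effect size will be quantified from the model using the difference in means between the groups with their associated 95% confidence intervals". Section 1.2 agrees on the endpoint: "The primary endpoint for Aim 2 will be the change in self-efficacy scores from baseline. Changes will be compared across arms". Neither section lists fixed effects, covariates, visit coding or a constraint on the baseline means, and no other section supplies them.

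The baseline score exists before allocation. Section 7.2.2 places it directly after consent: "The researcher will guide the subject through completion of the respiratory health questionnaire and self-efficacy assessment". Only after the fourth training session, if the participant qualifies, does it say that "the participants will be randomized to one of the two study arms". Self-efficacy is then repeated quarterly.

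The Randomization text in Section 7.1 describes a minimisation method that will "randomize participants based on demonstrated factors affecting prognosis". It lists time since diagnosis, age, latest FVC and, where available, FVC slope. Self-efficacy is not on that list.

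The time points are already set in Section 1.1. The primary hypothesis is that teams in the NRHC arm "report higher self-efficacy in the respiratory management of the disease at 6 months compared to those in the non-NRHC arm"; the secondary one begins "Patients in the NRHC arm report higher self-efficacy at 12 months". Sections 8.1 and 16.2 plan for up to 60 enrolled with a goal of 40 completing. The session count in Section 7.2.2 uses 20 subjects in the coaching arm.

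**The concern.** A raw change score subtracts the whole baseline value. Unless baseline and follow-up are almost perfectly correlated, that subtracts too much and adds the noise of the baseline measurement to the outcome. Using the baseline score as a covariate lets the data set how much to subtract, and under randomisation it estimates the same arm difference.

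Both arms perform weekly rPFT, so Aim 2 is the only comparison between randomised arms. It rests on about 20 completers per arm, which is a goal and not a certainty, and minimisation on the listed factors does not balance the self-efficacy score directly. What is at stake is the width of the confidence interval and the chance of detecting a coaching effect, not the validity of the result.

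**Working it through.** **The plan's own figure.** The only power statement, in Section 8.2, concerns FVC decline: 15 per arm, 80% power, effect size 0.95. A two-sample t-test at one-sided 0.05 gives 81.4%, and 15 is the smallest n that reaches 80%. At two-sided 0.05 it gives 70.9%. The plan does not state the level or sidedness. This is not a self-efficacy calculation, so there is no Aim 2 figure to reproduce and none is contradicted.

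**Inputs.** From the documents: N = 40 completers, n = 20 per arm, and a 6-month primary contrast. Assumed: outcome SD of 1 at each visit, and a baseline to month-6 correlation rho between 0.3 and 0.95.

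**Formulas for the variance of the arm difference.**

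- Change score: (2/n) × 2(1 − rho)
- Baseline-adjusted: (2/n) × (1 − rho²) × [1 + 1/(N − 4)]. The last factor is the price of estimating the baseline slope; at N = 40 it is 37/36.
- Ratio, adjusted to change: [(1 + rho)/2] × 37/36

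**Example, rho = 0.5.** Change: 0.1 × 1.0 = 0.100, SE 0.316. Adjusted: 0.1 × 0.75 × 37/36 = 0.0771, SE 0.278. Ratio 0.771.

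The detectable difference below is in SD units at 80% power, two-sided 0.05.

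| rho | SE, change | SE, adjusted | Variance ratio | Reduction | Detectable difference, change / adjusted | Change-score completers needed to match 40 adjusted |
|---|---|---|---|---|---|---|
| 0.3 | 0.374 | 0.306 | 0.668 | 33.2% | 1.076 / 0.879 | 60 |
| 0.5 | 0.316 | 0.278 | 0.771 | 22.9% | 0.909 / 0.798 | 52 |
| 0.7 | 0.245 | 0.229 | 0.874 | 12.6% | 0.704 / 0.658 | 46 |
| 0.8 | 0.200 | 0.192 | 0.925 | 7.5% | 0.575 / 0.553 | 44 |
| 0.9 | 0.141 | 0.140 | 0.976 | 2.4% | 0.407 / 0.402 | 41 |
| 0.95 | 0.100 | 0.100 | 1.002 | −0.2% | 0.287 / 0.288 | 40 |

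**Simulation check (20,000 replicates).** At 20 per arm the variance ratios are 0.66, 0.77, 0.88, 0.98 and 1.00 at rho 0.3, 0.5, 0.7, 0.9 and 0.95. At 15 per arm they are 0.68, 0.79, 0.89, 0.99 and 1.01. A separate run at 20 per arm gave 0.94 at rho 0.8.

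**Does a mixed model solve this by itself?** Not necessarily. With quarterly repeats, the large-sample month-6 ratio stays at (1 + rho)/2, where rho is the baseline to month-6 correlation. A random-intercept model with categorical visits and arm-by-visit terms (2,000 replicates, no loss) gave these mean month-6 SEs:

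| rho | Change as response | Baseline as covariate | Baseline as response, free mean per arm | Baseline as response, common mean |
|---|---|---|---|---|
| 0.3 | 0.371 | 0.302 | 0.372 | 0.300 |
| 0.5 | 0.315 | 0.275 | 0.316 | 0.272 |
| 0.7 | 0.243 | 0.226 | 0.244 | 0.224 |
| 0.8 | 0.200 | 0.191 | 0.200 | 0.189 |

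So the gain comes from a baseline covariate or a common baseline mean, not from the mixed model as such.

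**In power terms.** In the same model, with an assumed effect of 0.7 SD, baseline adjustment raises power from 44% to 60%, 59% to 71%, 81% to 86% and 93% to 95% at rho 0.3, 0.5, 0.7 and 0.8. With an assumed 8% loss per quarter it goes from 39% to 56%, 52% to 63%, 74% to 80% and 90% to 91%.

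**The case against.** The strongest reply is that silence is not a choice. Two sentences cannot list a model, and a baseline-adjusted model fits them. Change as the response with baseline as a covariate fits the wording exactly. It gives the same arm contrast as follow-up score with baseline as covariate, because subtracting baseline only shifts the baseline coefficient by one. All of this stands: the documents do not show that the sponsor decided against adjustment. But unadjusted readings fit the sentence equally well and are less precise over most of the range, and the text leaves the choice open.

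The reply that every size rests on an assumed rho also stands. So does the point that the figures apply to a visit-specific 6-month contrast; a model with linear time was not computed. The simpler factor (1 + rho)/2, which gives reductions of 35%, 25%, 15% and 10%, is a large-sample result and slightly overstates the gain at N = 40.

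Three stronger readings are tempting and unsupported.

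- **Bias or false positives.** A change-score comparison between randomised arms is valid. Its simulated type I error was 4.8% to 5.7%.
- **No primary time point.** Section 1.1 sets 6 months as primary and 12 months as secondary.
- **The minimisation factors must be in the primary model.** Section 7.1 calls them prognostic but does not show that they predict self-efficacy. If they explain 20% of follow-up variance only, adding four binary factors to the baseline model raises power from 71% to 80% at rho 0.5, and leaving them out makes the test conservative (type I error 3.0%). If they act equally on baseline and follow-up, power moves only from 71% to 73%. If they explain nothing, the full set with an indicator for missing slope can fall below the raw change score: 80% against 82% at N = 30 and rho 0.8.

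**Conclusion.** The point holds as a gap in precision and specification. Read literally, Sections 1.2 and 8.3 give a valid, unbiased change-score contrast that makes incomplete use of a baseline score the trial already collects. At 20 completers per arm, adjustment reduces the variance of the 6-month arm difference by about 33%, 23%, 13% and 7% at rho 0.3, 0.5, 0.7 and 0.8. The gain is negligible from about 0.9, and at 0.95 there is parity or a loss of about 1%.

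These sizes depend on the assumed rho, equal SDs at baseline and follow-up, equal arms and 40 completers. If the sponsor already intends a baseline covariate or a common baseline mean, there is almost nothing to gain and the plan only needs to say so. The change is worth making because it is nearly free, not because the stated analysis is wrong.

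**What to change.** In Section 8.3, state that the Aim 2 mixed model includes the baseline self-efficacy score as a fixed effect. Change as response with baseline as covariate is identical for the arm contrast, so the endpoint wording in Section 1.2 can stay. Baseline as a response with one common mean across arms is a practically equivalent alternative. Name the arm difference at 6 months with its 95% CI as the primary result and 12 months as secondary, carrying over Section 1.1. Use the same form for each respiratory score, with its own baseline.

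Adjustment for the minimisation factors, with an indicator for missing FVC slope, is not part of the primary fix. It may be an optional sensitivity analysis, with the full list of factors and their coding stated in advance.

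The cost is one or two sentences, one degree of freedom and no new data.

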9.0 Confidentiality, Privacy and Data Management

Please see HRP-598 Research Data Plan Review Form

10.0 Data and Safety Monitoring Plan

N/A

11.0 Risks

The risks posed to subjects in the study will be no different than those presented during standard of care administration of pulmonary function testing. In addition to guidance from the research team, those participating in remote assessments will be required to have a caregiver present to aid the patient in case assistance is required.

Loss of confidentiality is a risk of this study, but steps are taken to protect the participants' identities. Personal information, clinical assessments, test results, and survey responses will be labeled with a participant code assigned by REDCap and stored in this database. All data containing PHI will be collected either from the electronic medical record or in person. Data transmitted through the Air Smart Spirometer app will be labeled with the user's initials, gender, date of birth, and height, and ethnicity. Audio from telemedicine interactions during nurse coaching interventions may be stored on REDCap for review by a member of the research team. Video from telemedicine interactions and focus groups will not be stored.

12.0 Potential Benefits to Subjects and Others

12.1 Potential Benefits to Subjects

Participants in Part 2 may benefit from timelier recommendation of NIV support.

12.2 Potential Benefits to Others

This knowledge gained by this study may benefit those who are managed remotely using telemedicine. This will enable virtual care to be more equivalent to in-person care.

13.0 Sharing Results with Subjects

Participants will be informed of the results of their breathing tests at each visit. The respiratory therapist and nurse clinician will be responsible for making appropriate recommendations based on those results, and following up with the neurologist for NIV recommendation if necessary.

Participants will not be informed of overall study results unless they request it. Study results include the public presentation of research at academic conferences or through peer-reviewed journals.

14.0 Subject Stipend (Compensation) and/or Travel Reimbursements

There will be no compensation in Part 1. For Part 2, the patient participant will be compensated \$10 per month they are in the study, capped at a total compensation of \$120.

15.0 Economic Burden to Subjects

15.1 Costs

Subjects will incur no cost for their participation.

15.2 Compensation for research-related injury

It is the policy of the institution to provide neither financial compensation nor free medical treatment for research-related injury. In the event of injury resulting from this research, medical treatment is available but will be provided at the usual charge. Costs for the treatment of research-related injuries will be charged to subjects or their insurance carriers.

16.0 Resources Available

16.1 Facilities and locations

For Part 1, the consent procedure will be conducted within the ALS Clinic at [name] on the Hershey Medical Center campus. The clinic houses a room set up by the Penn State Hershey information technology department that is dedicated to ALS telemedicine. This room will also be used as the site for the respiratory therapist to conduct the rPFT assessment. This research room is in a private location and contains all the tools necessary for engaging in secure videoconferencing.

For Part 2, consent may be obtained in the ALS clinic or over the telemedicine interface. The home of the patient will be the site of most of the study procedures. When engaging in procedures via telehealth, a member of the study team will communicate with the participant from a private office or from a research room in the ALS clinic. The study team will exclusively use the HIPAA-compliant HMC Telemedicine system by AmWell that is used for routine clinical care of ALS patients.

16.2 Feasibility of recruiting the required number of subjects

We anticipate high interest in Part 1 due to the short time commitment and participation during a single clinical visit. We anticipate no issues recruiting 40 individuals for this study. The resource and timing limitations of Part 2 will make enrollment more challenging. We expect to screen and consent 60 participants, with the goal of having 40 participants meet the endpoint criteria. We anticipate the participation of two respiratory therapists to aid with rPFT administration.

16.3 PI Time devoted to conducting the research

The PI has devoted 25% time to oversight of this project, involving discussion the goals, procedures, analysis, and data review, as well as input on clinical matters as requested by members of the study team.

16.4 Availability of medical or psychological resources

If any medical or psychological resources are found to be needed during the course of the study, the participant will be directed to contact his/her Primary Care Provider or emergency care if warranted.

16.5 Process for informing Study Team

Before recruitment and any time a change is made to the protocol, the study team will meet to discuss changes in their role within the study, if applicable.

17.0 Other Approvals

17.1 Other Approvals from External Entities

N/A

17.2 Internal PSU Committee Approvals

Check all that apply:

- Anatomic Pathology – Hershey only – Research involves the collection of tissues or use of pathologic specimens. Upload a copy of HRP-902 - Human Tissue For Research Form on the “Supporting Documents” page in CATS IRB. This form is available in the CATS IRB Library.
- Animal Care and Use – All campuses – Human research involves animals and humans or the use of human tissues in animals

- Biosafety – All campuses – Research involves biohazardous materials (human biological specimens in a PSU research lab, biological toxins, carcinogens, infectious agents, recombinant viruses or DNA or gene therapy).
- Clinical Laboratories – Hershey only – Collection, processing and/or storage of extra tubes of body fluid specimens for research purposes by the Clinical Laboratories; and/or use of body fluids that had been collected for clinical purposes, but are no longer needed for clinical use. Upload a copy of HRP-901 - Human Body Fluids for Research Form on the “Supporting Documents” page in CATS IRB. This form is available in the CATS IRB Library.
- Clinical Research Center (CRC) Advisory Committee – All campuses – Research involves the use of CRC services in any way.
- Conflict of Interest Review – All campuses – Research has one or more of study team members indicated as having a financial interest.
- Radiation Safety – Hershey only – Research involves research-related radiation procedures. All research involving radiation procedures (standard of care and/or research-related) must upload a copy of HRP-903 - Radiation Review Form on the “Supporting Documents” page in CATS IRB. This form is available in the CATS IRB Library.
- IND/IDE Audit – All campuses – Research in which the PSU researcher holds the IND or IDE or intends to hold the IND or IDE.
- Scientific Review – Hershey only – All investigator-written research studies requiring review by the convened IRB must provide documentation of scientific review with the IRB submission. The scientific review requirement may be fulfilled by one of the following: (1) external peer-review process; (2) department/institute scientific review committee; or (3) scientific review by the Clinical Research Center Advisory committee. NOTE: Review by the Penn State Hershey Cancer Institute Scientific Review Committee is required if the study involves cancer prevention studies or cancer patients, records and/or tissues. For more information about this requirement see the IRB website at: <http://www.pennstatehershey.org/web/irb/home/resources/investigator>

